6.4.5 Transverse Microradiography

Sections, approximately 100 µm in thickness, will be cut parallel to the orientation cut (as shown in Figure 2), after completion of the SMH analysis, using a Silverstone-Taylor Hard Tissue Microtome (Scientific Fabrications Laboratories, USA). The sections will be placed in the TMR-D system and X-rayed at 45 kV and 45 mA at a fixed distance for 12 s. An aluminium step wedge will be X-rayed under identical conditions. The digital images will be analyzed using the TMR software v.3.0.0.18. Sound enamel will be assumed to be 87% v/v mineral.

Lesions will be analyzed after *in situ* demineralization and the following three parameters calculated:

- 1. Integrated Mineral Loss ΔZ = [(lesion depth x 87) area under the curve*]
- 2. Lesion Depth L (83% mineral i.e. 95% of the mineral content of sound enamel)
- 3. Maximum mineral density at the surface-zone SZmax

Note: *area under the curve which relates volume % mineral at distances from the specimen surface with respect to section thickness.

6.5 Laboratory Data

After the analyses are completed, all enamel specimen surface microhardness, transverse microradiography and enamel fluoride uptake data will be reviewed by the principal investigator before transfer to the statistician. The investigator will document this review and documentation will be filed with the laboratory study files.

6.6 Specimen Retention

Laboratory specimens will be retained by the study site for twelve months following database lock.

7. STATISTICAL ANALYSES AND SAMPLE SIZE JUSTIFICATION

7.1 Statistical Analyses

The mean % SMH recovery will be calculated using the four sets of indentations within each enamel specimen. The mean fluoride uptake will be calculated using the four samples within each enamel specimen. The mean % SMH recovery, mean fluoride uptake, mean acid resistance and mean ΔZ , L, SZ_{max} will be computed for the two enamel specimens within a subject by treatment; if a subject is missing an enamel specimen, the available enamel

specimen will be used. Analyses of fluoride uptake will be performed after using a natural logarithm transformation because the measurements generally are not normally distributed.

The treatments will be compared using analysis of variance models (ANOVA) suitable for a crossover study. The models will include random effects for subject and fixed effects for study period, and product. The random effects will model the correlation and variances over time between treatments. The primary comparison of interest will be to determine if the test treatment to be statistically significant compared to the positive control treatment. Secondary comparisons will be to determine if the test treatment to be statistically significant compared to the negative control treatment and if the positive control treatment to be statistically significant compared to the negative control treatment. A 5% significance level will be used for all tests. No alpha-level adjustments for multiple comparisons adjustments will be applied.

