4. TEST TREATMENTS

The following products applied with a provided, marketed toothbrush will be used in this study:

- 1. 0 ppm F (placebo, negative control): Tom's of Maine Silly Strawberry
- 2. 1100 ppm F as NaF (positive control): Crest Cavity Protection Toothpaste
- 3. 1100 ppm F as NaF Test Product: Pronamel Daily Protection

All three test products will be purchased by Haleon and supplied to OHRI as part of the ISS process.

The toothpaste tubes will be wrapped in opaque adhesive label to conceal product identity containing the study number, a code letter that is assigned by the Study Statistician for identifying the product, a caution statement, and a phone number to call in the case of an adverse response. Subjects will also receive an Oral-B Indicator 35 Soft Toothbrush, rinsing cups, and a timer.

Label:

Study # 23-I-121

Directions for use: Use only this toothpaste & toothbrush provided, brush daily after breakfast and before going to bed for one minute using a full ribbon of toothpaste. Rinse with 15 ml of water for 10 seconds using the marked cup provided.

Keep out of the Reach of Children
For Clinical Trial Use Only
Oral Health Research Institute, [name]
Emergency Contact # [contact]

Subjects will also receive a placebo toothpaste and standard toothbrush for home use during the 2- to 3-day lead in period.

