7.2 Sample Size Justification

Based on previous studies we estimate the standard deviation of the differences between treatments in the crossover model to be 20 for % SMH recovery. With a sample size of 58 subjects completing the study, the study will have 80% power to detect a difference between any two treatments of 7.5 for % SMH recovery, assuming two-sided tests each conducted at a 5% significance level. Due to expected dropouts during the crossover study, the study will enroll 65 subjects.

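### Does leaving the covariance structure of the crossover model unnamed put the 5% level of the test versus positive control comparison at risk?

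*Combined protocol and SAP*

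**What the plan says.** Section 7.1 gives the model terms: "The models will include random effects for subject and fixed effects for study period, and product". The next sentence describes the covariance: "The random effects will model the correlation and variances over time between treatments". On the target of inference it says: "The primary comparison of interest will be to determine if the test treatment to be statistically significant compared to the positive control treatment". The level is the same everywhere: "A 5% significance level will be used for all tests". The outcomes averaged over the two specimens per subject and product, to which this modelling applies, include "The mean % SMH recovery, mean fluoride uptake, mean acid resistance" and the three microradiography measures. Fluoride uptake is log-transformed first.

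Section 7.2 gives the only variance in the documents: "we estimate the standard deviation of the differences between treatments in the crossover model to be 20 for % SMH recovery". With 58 completers it claims "80% power to detect a difference between any two treatments of 7.5 for % SMH recovery", two-sided at 5%.

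Section 4 lists the three products: a 0 ppm F placebo, and two pastes that each carry 1100 ppm F as NaF.

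**The concern.** The wording of Section 7.1 admits at least three models: one random subject intercept, a covariance indexed by period, and a covariance indexed by product. They need not give the same p-value for the primary comparison.

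The simplest of them, a single subject effect, pools error over all three products. Two of the three pairwise differences that feed the pooled error involve the placebo, which has no part in the comparison of the test paste with the positive control. If subjects respond to a fluoride-free paste with a different spread, or if placebo responses track fluoride responses differently from how the two fluoride pastes track each other, the standard error of the primary comparison is wrong. The test is then conservative or liberal. The same could happen for fluoride uptake, acid resistance and microradiography, for which no variances are given. A structure left open can also be chosen after the data are seen.

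**Working it through.** **Inputs.** From Section 7.2: SD of within-subject differences 20, difference 7.5, 58 completers, two-sided 5%, power 80%. From Section 7.1: random subject, fixed period and product. Assumptions: complete data; the six treatment orders used about equally often in the simulations. The documents give no pair-specific SDs or correlations, so those are varied.

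**Step 1: the plan's own figure.** The standard error is 20/√58 = 2.626, so the noncentrality is 7.5/2.626 = 2.856. Power from the noncentral t depends only slightly on the error term:

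- Pooled ANOVA, df = 174 − 1 − 57 − 2 − 2 = 112: 80.8%.
- Paired t, df = 57: 80.2%.
- Period-adjusted analysis of the two products compared, df = 116 − 58 − 2 − 1 = 55: 80.1%.

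The stated 80% is reproduced under any of these, so the sample size does not depend on which structure is fitted.

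**Step 2: the pooled error.** Let V_TP, V_T0 and V_P0 be the variances of the three pairwise differences (T test, P positive control, 0 placebo). With one random subject effect and complete data, the model estimates the variance of every pairwise difference by V̄ = (V_TP + V_T0 + V_P0)/3. The estimated standard error for test versus positive is therefore too large or too small by the factor r = √(V̄/V_TP), and the true level is about 2Φ(−1.96 r).

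Fix the test-positive SD at 20 and give both placebo pairs a common assumed SD. Simulated values are from 40,000 trials each.

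| Placebo-pair SD | V̄ | r | Level, formula | Level, simulated | Power at 7.5, simulated |
|---|---|---|---|---|---|
| 16 | (400 + 2×256)/3 = 304 | 0.872 | 8.8% | 8.7% | 86.7% |
| 17 | 326 | 0.903 | 7.7% | 7.7% | 85.6% |
| 20 (the plan) | 400 | 1.000 | 5.0% | 5.2% | 80.8% |
| 23 | 486 | 1.102 | 3.1% | 3.1% | 74.9% |
| 25 | 550 | 1.173 | 2.2% | 2.2% | 70.6% |
| 30 | 733 | 1.354 | 0.8% | 0.8% | 57.4% |

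Unequal placebo pairs with SDs 14.1 and 24.5, which leave V̄ at 400, gave 5.1%. So equality of the pair with the average is what matters, not equality of all three. An analysis using only the test and positive-control data stayed at 4.8% to 5.3% in every setting, with power of about 80%.

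**Step 3: what would produce a departure.** Give both fluoride pastes unit SD, the placebo SD s, correlation a between the fluoride pastes and b between placebo and either fluoride paste. Then V_TP = 2(1 − a) and V_T0 = V_P0 = 1 + s² − 2bs.

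| s | a | b | V_TP | V_T0 | r | Level |
|---|---|---|---|---|---|---|
| 1 | 0.6 | 0.4 | 0.80 | 1.20 | 1.155 | 2.4% |
| 1.5 | 0.4 | 0.4 | 1.20 | 2.05 | 1.213 | 1.7% |
| 0.5 | 0.4 | 0.4 | 1.20 | 0.85 | 0.898 | 7.9% |
| 0.5 | 0 | 0 | 2.00 | 1.25 | 0.866 | 9.0% |
| 0.5 | 0.75 | 0.75 | 0.50 | 0.50 | 1.000 | 5.0% |
| 0.5 | 0.6 | 0.4 | 0.80 | 0.85 | 1.021 | 4.6% |
| 1 | 0.4 | 0.6 | 1.20 | 0.80 | 0.882 | 8.4% |
| 1 | 0.4 | 0.7 | 1.20 | 0.60 | 0.816 | 11% |

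With equal SDs (s = 1), inflation needs b > a: placebo closer to each fluoride paste than the two same-strength NaF pastes are to each other. Nothing in the documents suggests that ordering, and the reverse is conservative. A less variable placebo (s = 0.5) inflates the level to 7.9% when all correlations are 0.4. If the two fluoride pastes are instead correlated 0.6 with each other and 0.4 with placebo, the level is 4.6% and nothing is inflated. The sign thus depends on SDs and correlations jointly, and none of these is known.

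**The case for a change.** The strongest case for acting is that the mathematics is certain and the edit is nearly free. A covariance left unstructured and indexed by product, with Kenward-Roger degrees of freedom, held the simulated level at 4.7% to 5.3% in every complete-data setting tried. If the variances are equal it costs under one power point (80.8% to 80.2%). Indexing by period would not help: with balanced orders it averages back to the same pooled value, so the index matters. Naming the structure before the laboratory data reach the statistician would also close off a later choice.

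The pooled-error algebra stands, and so does the observation that Section 7.1 names no structure. What does not stand is the step from there to a fault in the primary test. That step needs the single-intercept reading, under which there would be one common variance and one common correlation, and the plan's reference to variances between treatments would say almost nothing. It also needs unequal pairwise variances, whereas Section 7.2 applies one SD to any pair. For the other outcomes no variance is available on either side of the argument. The log transformation of fluoride uptake, adopted for non-normality, will also alter how spread differs across products. Finally, the three-pair average is exact only with complete data, and 65 subjects are enrolled to obtain 58 completers.

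**Conclusion.** No change to the plan is needed. Section 7.1 leaves out a technical detail, and its own sentence on correlation and variances points the analyst to a sensible way of filling it. Under the plan's stated assumption of one SD of 20 for any two products, the level is 5% and power is 80.2% to 80.8%, whichever error term is used. A departure needs both a single-intercept fit and unequal pairwise variances. In the assumed settings the level then ranges from 0.8% to about 11%, and the documents give no basis for choosing among them or for saying whether the test would be liberal or conservative. An analyst who fits product-specific variances, or who analyses the within-subject difference for the pair compared, gives up less than one power point and needs no more subjects. These figures rest on complete data and near-balanced orders.

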7.2 Sample Size Justification

Based on previous studies we estimate the standard deviation of the differences between treatments in the crossover model to be 20 for % SMH recovery. With a sample size of 58 subjects completing the study, the study will have 80% power to detect a difference between any two treatments of 7.5 for % SMH recovery, assuming two-sided tests each conducted at a 5% significance level. Due to expected dropouts during the crossover study, the study will enroll 65 subjects.

8. DATA QUALITY ASSURANCE

This study will be conducted in compliance with the US Code of Federal Regulations (CRF) governing informed consent (21 CFR 50), Institutional Review Board (IRB) (21 CFR 56), and with applicable regulations governing Investigator conduct (21 CFR 312).

9. OBLIGATION OF THE INVESTIGATOR

9.1 Advertising

All potential advertising materials used to recruit subjects for this study will be submitted to the relevant IRB.

9.3 Subject Consent

Written informed consent will be obtained from all subjects prior to their enrollment into the study. The consent form will comply with all applicable regulations governing protection of the participants in the study, and include basic elements specified in the US. Code of Federal Regulations, 12 CFR 50.25(a). A signed copy of the consent form will be given to the subject and the original one will be retained by the Investigator. In order to ensure confidentially, the Investigator will store the consent forms separate from the CRFs.

9.4 Data Collection

Data will be collected on source documents/CRFs created by the Investigator.

9.4.1 Case Report Forms

Case report forms will be used for recording all data not entered directly into computers. The Investigator will be responsible for maintaining original consent forms, CRFs and other source documentation.

The CRFs that will be used, unless otherwise indicated are:

- Inclusion/Exclusion Criteria
- Continuance Criteria
- Oral soft tissue
- Oral hard tissue
- Adverse event
- Serious adverse event
- Subject Accountability

9.5 Adherence to Protocol

The final protocol constitutes the conduct of the study. The Investigator is required to adhere to this final protocol. Any reasonable alternatives, variations, or deviations from the protocol must first be approved by the IRB. Any clarification to the protocol will be documented in the study file.

9.6 Records Retention

At the conclusion of the study, all records, relevant medical/dental records, copies of CRFs, and informed consent forms for all subjects treated with the drug or employed as a control in the study are retained by the Investigator for 15 years.

9.7 Investigator's Final Report

Following the completion of the study the Investigator shall prepare an integrated clinical and final study report. The final report will include a general description of the conduct of the study including protocol deviations, subject withdrawals, a discussion of AEs, safety data, and laboratory analysis. This report will be approved and signed by the Investigator.

